### **Diabetic Nephropathy and End-Stage Renal Disease**

The group has published extensively on various aspects of diabetic nephropathy and ESRD (19,20,29,48,49). Recently, we have investigated the risk of renal failure and death in individuals with parental T1D, i.e., having parents with the same disease, finding slightly higher mean glycated haemoglobin and a higher risk of renal failure. Also, women with parental T1D, but not men had higher risk of premature death (50).

### **Socioeconomic Circumstances and Health Outcomes**

We have researched socioeconomic disparities between individuals with and without T1D both in aetiological and prognostic studies, see (29,30,49,51,52) for some examples. Most recently, we have investigated socioeconomic exposure during childhood and impact on glycaemic control in the individual as an adult. Preliminary data show that HbA1c is higher if the individual lived in household that received income support (effect size 0.45 SD), unemployment benefits (effect size 0.19 SD) or if the parents had less than 12 years of education (effect size 0.46 SD).

### **Health Economics and Type 1 Diabetes**

Research from our group and its collaborators has demonstrated positive trends in T1D complications, including a decline in ESRD incidence (20,49). Additionally, we have explored the socio-economic consequences of T1D (52,53), developed risk equations for Type 2 Diabetes (54) and validated health-economic models (55). Ongoing work at the Swedish Institute for Health Economics (secondary affiliation of co-applicant [name]) includes the development of a health-economic model for T1D, initially focusing on adults (40) but with plans to incorporate childhood and adolescent risks for a full lifespan perspective. Preliminary data indicate that T1D in children has lasting effects on parental labour-market outcomes, suggesting a need to integrate a family impact module into health-economic models.

### **Case-Control and Cohort Registers as a Part of Statistical Method Development**

Our group has extensive experience in developing statistical methods for observational studies. Since 2009, our team has advanced theoretical frameworks related to causal inference in disease incidence data, see (49,56–59) for some examples. Research has alternated between applied and theoretical studies, with particular focus on the design and methodologies used in the SCDR.

### **Equipment**

---

The Swedish Childhood Diabetes Register (SCDR) started for research purposes and records virtually all incident cases of childhood-onset T1D (0-14 years) since 1 July 1977 (47). The SCDR includes more than 24 000 cases and for each case there are four controls matched for age and municipality at the time of T1D diagnosis. In 2008, the SCDR was linked to several national registers to create a comprehensive database. These registers include the Swedish Renal Register (SRR), the Medical Birth Register (MBR), the National Patient Register (NPR), the Cause of Death Register (CDR), the Prescribed Drug Register (PDR), the Cancer Register (CR), the Integrated Database for Labour Market Research (Swedish acronym LISA) and the Multiple Generation Register (MGR). The SCDR is also collaborating with the National Diabetes Register (NDR). For this project, particularly hypothesis 1, we will link SCDR to the Child Health Services Register (CHS).

The SCDR database has been updated with longitudinal data several times, most recently in 2023. It is stored and administered at the Umeå University SIMSAM-laboratory.

### Project Description

---

The SCDR, initially established through collaboration with all Swedish paediatric diabetes clinics, collected clinical data until 2010 (4). Since then, the National Board of Health and Welfare has provided incident data via the Prescribed Drug Register (PDR) (6). An interdisciplinary team has long been engaged in SCDR research, encompassing expertise in paediatric diabetes medicine, general medicine, molecular biology, endocrinology, nephrology, statistics, and health economics. PhD students from multiple institutions contribute to this work. The SCDR research project is registered at ClinicalTrials.gov with identifier NCT06883318.

#### **Hypothesis 1: The incidence of childhood-onset type 1 diabetes will peak in Sweden during the early 2020s.**

To deepen our knowledge on incidence trends and understand more of age-period and cohort effects in T1D incidence trends, we will make use of hierarchical Age-Period-Cohort (APC) analysis with covariates, see e.g. (60) for a comprehensive overview. Incident cases come from the PDR and covariates will come from the MBR concerning early pregnancy weight and gestational age and from the CHS regarding child growth (61). We will expand our previous analysis using non-linear semiparametric generalized additive models for count data (4,6). The time related changes we study are age effects (A), period effects (P) and shared life events for a set of individuals, i.e., cohort effects (C). The fitted APC models can be evaluated with model diagnostics and give (i) the magnitude of the individual APC effects. For example, the minimum and maximum values of the marginal APC effects and the overall size of each effect, (ii) an assessment of one-dimensional covariate smooth effects, for example for child weight or mother's weight respectively, and (iii) a table with full model results. Either a list of several models or for a single model, here both linear coefficients and all nonlinear estimates are returned. The work will resume during the latter part of the period, with IW and TL leading.

---

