#### **1. Time trends in childhood-onset type 1 diabetes:**

- To examine time, age and cohort effects on the incidence of childhood-onset T1D in Sweden.
- To identify environmental and lifestyle-related risk factors contributing to the increasing incidence of T1D.
- To assess the potential impact of early-life exposures, including pre- and perinatal factors and early childhood infections, on the development of islet autoimmunity and T1D.

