### Time Trends in Childhood-onset Type 1 Diabetes

The aetiology of childhood-onset type 1 diabetes (T1D) is multifactorial, arising from a complex interaction between genetic predisposition and environmental risk factors (1,2). In contrast to other autoimmune diseases, T1D predominantly affects younger populations (3). Between 1978 and 2008, the incidence of T1D among children below 15 years in Sweden more than doubled (4). Consequently, alongside asthma, T1D has become one of the most prevalent chronic diseases among children in Sweden. Similar upward trends in incidence have been documented in numerous other countries (5). Over the past decade, the incidence has remained high but stable (Figure 1) (6).

[figure not shown]

Figure 1: The incidence childhood-onset type 1 diabetes in Swedish, foreign and total population 0-15 years divided on boys (a) and girls (b), dots being incidence and lines being predicted incidence from a general additive model (GAM) for Poisson response (6).

The rapid increase in the incidence of childhood-onset T1D can only be attributed to a rise in non-genetic, lifestyle-related risk factors (7). The peak incidence of autoimmunity against insulin-producing  $\beta$ -cells occurs in the second year of life (8), suggesting that environmental triggers likely operate very early, either in utero or during early childhood. A wide range of environmental risk factors have been investigated (2), with several pre- and perinatal factors consistently associated with T1D risk, including maternal obesity, preterm birth, and postnatal growth (9,10). Infections, particularly viral infections, have also been implicated in T1D pathogenesis (11), although their population-level impact is harder to study due to the frequent lack of diagnosis or aetiological identification of childhood infections. Some prospective studies have found associations between respiratory infections and islet autoimmunity (12), whereas others have not (13). During the COVID-19 pandemic, reports indicated an initial rise in T1D incidence followed by a subsequent decline, a trend less pronounced in younger children (14,15). Preliminary data from Sweden suggest similar patterns, though these observations require confirmation through extended follow-up and analysis. A whole-population study in Denmark (16) found no association between SARS-CoV-2 infection and subsequent T1D risk in children, whereas a preliminary report from Norway described a 60% risk increase (17).

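### Hypothesis 1 promises separate total sizes for the age, period and cohort effects, but their linear parts cannot be identified from incidence data

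*Protocol*

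**What the plan says.** Protocol, Project Description, Hypothesis 1, plans a hierarchical age-period-cohort (APC) model with covariates from the birth and child health registers, extending the group's earlier additive models for counts. The first output it lists is "the magnitude of the individual APC effects", illustrated by "the minimum and maximum values of the marginal APC effects and the overall size of each effect". The third is a table of full results, of which it says "here both linear coefficients and all nonlinear estimates are returned". It adds: "The fitted APC models can be evaluated with model diagnostics".

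This work serves the first bullet of research area 1 under Purpose and Aims: "To examine time, age and cohort effects on the incidence of childhood-onset T1D in Sweden".

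On the data, Hypothesis 1 states "Incident cases come from the PDR". The opening of Project Description says that clinical data were collected until 2010 and continues: "Since then, the National Board of Health and Welfare has provided incident data via the Prescribed Drug Register".

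The protocol does not mention that the three time scales are linearly dependent. It names no constraint, and it does not limit the reported sizes to the parts that can be identified.

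**The concern.** An overall size, or a minimum and maximum, includes the linear trend of an effect. That is the part of an APC model that no data window can identify. A random-effects or penalised fit still returns numbers, but the division of the trend between period and cohort comes from the fitting rule.

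The distinction matters for interpretation. A birth-cohort trend points towards early-life exposures and a period trend towards influences acting in calendar time. If the first output is read as the answer to the aim, a cohort trend can be reported as a period trend, or the reverse. Model diagnostics would give no warning, because the competing decompositions fit the same rates.

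**Working it through.** The protocol gives no figure to reproduce here. The algebra needs no assumptions. The numbers only illustrate its size and are not register estimates. RR means largest divided by smallest effect.

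**1. Algebra.** Let a, p and c be age, period and cohort, with linear slopes α, π and κ. Since p − a − c = 0, adding δ(p − a − c) changes no rate, so (α, π, κ) and (α − δ, π + δ, κ − δ) fit identically. The net drift π + κ does not change, and neither do departures from linearity or the fitted rates.

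**2. Rank.** With single years and ages 0-14, the 2011-2023 design has 1 + 14 + 12 + 26 = 53 columns and rank 52. Other windows are also one short: 56 of 57 (2011-2025), 62 of 63 (2006-2023) and 118 of 119 (1978-2023). A longer series does not help.

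**3. The protocol's own trend.** The Survey of the Field states: "Between 1978 and 2008, the incidence of T1D among children below 15 years in Sweden more than doubled". Taking exactly a doubling over 30 years, the slope is ln 2 / 30 = 0.0231 a year. For 1978-2008 the spans are 14 years of age, 30 of period and 44 of cohort. RR = exp(slope × span) for the linear part of each effect, with the same fitted rates in every row:

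| Trend assigned to | Age RR | Period RR | Cohort RR |
|---|---|---|---|
| Period | 1.00 | 2.00 | 1.00 |
| Half each | 1.18 | 1.41 | 1.66 |
| Cohort | 1.38 | 1.00 | 2.76 |

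**4. Hierarchical fit.** Assumptions: 2011-2023 (the start follows from the change of data source, the end is assumed); log-rate 0.05(a − 7) − 0.006(a − 7)² plus linear terms; Poisson counts; crossed random period and cohort effects; no covariates. The 640 cases a year come from spreading the 24,000 cases given under Equipment over mid-1977 to end 2022 (end assumed), with counts doubling linearly over 1978-2008 and then flat. The plain average is 24,000 / 45.5 = 527, and 800 was taken as an upper value.

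| Truth | Fitted period RR | Fitted cohort RR |
|---|---|---|
| Pure cohort, +2% a year | 1.25 | 1.02 |
| Pure period, +2% a year | 1.25 | 1.02 |
| No trend | 1.02 | 1.03 |
| Period +2%, cohort −2% | 1.01 | 1.02 |
| Period −2%, cohort +2% | 1.02 | 1.02 |

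- In the pure cohort case the trend went to period, and the fitted age slope fell from 0.050 to 0.030, as step 1 predicts with δ = 0.02.
- In the last two rows the true RRs are exp(0.02 × 12) = 1.27 for period and exp(0.02 × 26) = 1.68 for cohort.
- At 527 or 800 cases a year the pure-trend results stay at 1.24-1.26 for period and 1.02-1.03 for cohort.
- At 1% a year, pure cohort gives 1.07/1.04 and pure period 1.10/1.02 (period/cohort, 20 runs).

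**5. Variance assumption.** The 2% trend was fitted to noise-free expected counts with the random-effect SDs fixed. Period/cohort SDs of 0.3/0.03 give RRs of 1.27/1.00 (deviance 0.01). SDs of 0.03/0.3 give 1.02/1.43 (deviance 0.86-0.87). Both hold under either truth, on 15 × 13 = 195 cells.

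**6. Cohort grouping.** A separate check used log-rates for 1978-2023, slope 0.0231, residual SD 0.14 and estimated variance components, with one simulated data set per truth. One-year cohort groups gave period/cohort RRs of 2.75-2.85/1.02-1.07. Five-year groups gave 1.00-1.02/3.33-3.40. The ranges cover pure period, pure cohort and half-and-half truths.

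**7. Marginal averages.**
- Averaging over observed cells gives a cohort RR of 2.08 with no period or cohort effect at all (1.32 to 4.06 across assumed age slopes), because the oldest cohorts are seen only at older ages and the newest only at young ages.
- Balanced averages over all 15 ages remove that artefact. The period slope and the cohort slope then both equal the net drift, 0.020, under either truth.
- In 1978-2023, the 32 cohorts seen at all ages give RR exp(0.02 × 31) = 1.86 under either truth.

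**8. What survives.** Net drift, from age as a factor plus linear year (500 runs), is 0.0202 (SD 0.0030) under pure cohort and 0.0198 (SD 0.0029) under pure period.

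**The case against.** The algebra is not in dispute. The case for leaving the text alone runs as follows.

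- **The sizes are only examples, and marginal effects are legitimate descriptive summaries.** Once a rule is fixed they are indeed reproducible. But observed-cell averages can show a cohort effect where none exists, and balanced averages give both effects the same slope, so neither attributes the trend.
- **The protocol never says the sizes will decide between causes.** That is correct. It does present individual magnitudes as what the models give, under an aim of examining the three effects, with nothing to stop that reading.
- **Constraint, grouping and penalty belong in an analysis plan.** They do, but a constraint chosen there is still an assumption. The difficulty is a promised result that no later choice can turn into a finding from the data alone.
- **The linear coefficients in the third output may be only ordinary parametric covariate terms.** This is a fair reading, so that part of the fix is conditional.
- **The 2% drift does not match the protocol's own account of a stable past decade.** This stands as a limit on the first two rows of the hierarchical illustration. Under stability the fitted ratios were near 1, and harm there needs opposing trends that cancel, for which the protocol gives no evidence. The observed-cell artefact arises even when nothing changes.
- **The planned covariates were not simulated.** This also stands. They may explain part of a trend, so the ratios are not forecasts of error, but they do not identify the linear split that remains.

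**Conclusion.** The point holds. For any data window, the total sizes of the separate effects cannot tell a linear period trend from a linear cohort trend. That conclusion is algebraic.

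How far a reported size could mislead depends on the drift and on the rule used. In the illustrations, one set of rates supports period/cohort ratios from 1.27/1.00 to 1.02/1.43. Those figures rest on the assumed age curve, slopes, end year and case numbers, without covariates.

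The defect is confined to attributing the trend under research area 1. The Hypothesis 1 claim of a peak concerns fitted incidence by calendar year and stands, as do the net drift and the departures from linearity. The text should be changed, but the planned models need not be.

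**What to change.** In the first output of Hypothesis 1, make these the main results:

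- the net drift (period plus cohort slope);
- period and cohort departures from linearity;
- fitted age-specific and age-standardised annual incidence.

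If separate total sizes are still shown, or if the third output includes linear age, period or cohort coefficients, state the constraint or averaging rule, label the figures as dependent on it, and say that they will not be used to favour a period or a cohort cause.

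The cost is a few lines of text and some extra summaries from models already planned. No new data are needed. The price is that total period and cohort effects can no longer be quoted as single, assumption-free figures.

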#### **Hypothesis 2: The incidence of ESRD, caused by T1D, will stabilize at a low level but we will see a delayed peak incidence in ESRD, with pregnancy as a significant risk factor in women.**

Both socioeconomic background and sex are important mediators of risk to develop ESRD and can also be important for survival in RRT. Another important determinant of survival in RRT is the mode of treatment, where early renal transplantation is associated with increased survival (25). The SCDR is regularly linked to the SRR, allowing analyses of ESRD incidence by duration of diabetes, age and gender. In the coming years, part of our population will have reached post-menopausal age, and we have the possibility to follow-up on renal failure and ESRD with respect to differences between men and women in different ages. Linkage to LISA allows further analyses on socioeconomic risk determinants and region of living, linkage to the PDR will allow us to study effects of antihypertensive medication and linkage to the MBR will give data on pregnancy circumstances. We will use conventional life table and Cox regression but also more recent proposals from causal survival analysis. These studies will be performed in collaboration with [name] and [name] at SRR, Jönköping. In 2024, the most recent SRR data was added to the SCDR. Analytic work can commence in early 2026.

---

**Hypothesis 3: Glycaemic control is on the causal pathway linking socioeconomic status during childhood and long-term complications in adults with childhood-onset T1D. Family health shocks such as a child with T1D negatively affects the health of siblings.**

In these cohort studies, we identify parents and siblings through the MGR. Exposure data on parents' educational level, income, well-fare support and other socioeconomic circumstances come from LISA. Outcome data on glycaemic control and other clinical parameters (blood pressure, weight, urine-albumin, etc.), come from the NDR; we take data on pharmacologic treatment from the PDR and data on long-term complications from the NPR and the SRR. To account for repeated measures of glycaemic control and also perform variable selection, we will use a penalized generalized linear mixed model approach (62,63).

In the analysis on the siblings, we use pharmacological information from the PDR, specifically data on antidepressants and compare them to non-related controls. We will retrieve health data from the NPR and the CDR and use LISA for socioeconomic variables. We will apply a non-parametric approach, focusing on population effects with analyses based on Persson et al (58). Both these studies will involve PhD-student [name].

---

**Hypothesis 4: Health-economic evaluation models require risk equations tailored for integration into Markov and microsimulation models. These equations must capture T1D-related complications and outcomes from childhood through middle age, reflecting current diabetes management practices.**

Modern T1D management has improved outcomes for individuals diagnosed in childhood, as well as their parents. We will use NPR data to develop a comprehensive set of risk equations predicting a wide range of T1D-related outcomes, including micro- and macrovascular complications such as myocardial infarction, stroke, heart failure, peripheral vascular disease, hypoglycaemia, hyperglycaemia, amputation, end-stage renal disease, and retinopathy. These analyses will incorporate time-to-event methods and assess excess risks for additional comorbidities, including psychiatric conditions and all-cause hospitalisations. Mortality risk estimates will also be included.

Risk factors such as age, diabetes duration, and clinical variables (e.g., HbA1c) will be considered. Sensitivity analyses will evaluate changes in risk estimates over time in response to evolving treatment recommendations. Additionally, the impact of T1D onset on parents will be examined using hospitalisation data (NPR) and employment-related records (LISA). We will compare T1D parents to control parents, adjusting for confounders such as sibling number, age, employment, and education using panel-data regression methods. This work, led by [name], will involve a PhD student based at Lund University with proximity to modelling expertise at the Swedish Institute for Health Economics (<https://ihe.se/>).

---

**Hypothesis 5: Target trial protocols can be specified for research questions lacking a pre-defined time zero, allowing for both cohort and case-control study designs in the SCDR. For research questions related to disease-free controls, a case-control sample analogue can be given.**

This project will address methodological challenges in defining time zero when emulating a target trial. Key challenges include specifying eligibility criteria, treatment strategies, and treatment assignment while ensuring appropriate follow-up. We will define causal contrasts (intention-to-treat and per-protocol effects) and outline statistical analyses suited to target trial, cohort, and case-control studies.

We will follow the TTE framework (46) and focus on Emulation Failure 1 (Figure 2). Statistical methodology will be developed using standard inference, causal inference, and epidemiological methods adapted for TTE applications. Research will progress in three phases: First, analytical methods will be developed. Second, these methods will be integrated into computer software, followed by testing with simulated data. Finally, the methods will be applied to the SCDR data. In the final phase, interdisciplinary collaboration will extend beyond epidemiology and statistics to incorporate expertise from education and health sciences, addressing real-world challenges. The project will involve IW and EP in phases one and two, with TL and AM contributing to the final phase to contextualise the empirical findings.

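### Does Hypothesis 2 lack the clinical measurements needed to study antihypertensive and pregnancy effects on ESRD?

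*Protocol*

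**What the plan says.** The heading of Hypothesis 2 (Protocol, Project Description) predicts that ESRD will settle at a low level with a later peak, "with pregnancy as a significant risk factor in women". The text then goes through linkages by purpose: the SRR for counting ESRD by duration, age and sex; LISA for socioeconomic position and region; and, for the two exposures at issue, "linkage to the PDR will allow us to study effects of antihypertensive medication and linkage to the MBR will give data on pregnancy circumstances". On methods it says: "We will use conventional life table and Cox regression but also more recent proposals from causal survival analysis". It lists no adjustment variables.

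Hypothesis 3 states that "Glycaemic control is on the causal pathway linking socioeconomic status during childhood and long-term complications in adults with childhood-onset T1D". It draws glycaemic control and other clinical values from a further register ("blood pressure, weight, urine-albumin, etc.), come from the NDR") and takes "data on long-term complications from the NPR and the SRR".

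The Equipment section describes one database linked to several national registers, among them "the Cause of Death Register (CDR") and the NPR. It adds: "The SCDR is also collaborating with the National Diabetes Register (NDR").

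**The concern.** Antihypertensives are prescribed because of raised blood pressure or albuminuria, and both also predict ESRD. Whether a woman with type 1 diabetes becomes pregnant may depend on her kidney function and glycaemic control. The protocol's own reasoning makes these variables matter. Hypothesis 3 puts glycaemic control on the path to complications, and the Survey of the Field suggests that the fall in ESRD may reflect better diabetes and blood pressure management.

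Read as a complete list, the Hypothesis 2 sources hold none of these measurements, and no survival method can adjust for values absent from the data. A medication hazard ratio would then mix the drug effect with the reason for prescribing. A pregnancy hazard ratio would mix pregnancy with the health that preceded it. The stakes are real, because the Survey of the Field expects evidence on this question to inform advice to women with type 1 diabetes.

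A smaller worry is that the life table is named without saying how death before ESRD is handled. If deaths are censored and the result is read as cumulative risk, that risk is overstated.

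**Working it through.** The protocol gives no sample size, event count or effect size for Hypothesis 2, so there is no stated figure to reproduce. The question is whether the register list is closed, and what would follow if it were.

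**Is the list closed?**

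1. Hypothesis 2 says what particular linkages make possible. It does not say that only these will be used.
2. Hypothesis 4 names only the NPR as the source for its risk equations, yet counts HbA1c among the risk factors to be considered. The register sentences are therefore not inventories.
3. Hypothesis 2 also discusses survival on renal replacement therapy without naming the Cause of Death Register, which Equipment lists as linked. (The protocol does not say whether the SRR itself supplies deaths, so this is a weaker sign.)
4. The NDR is available to the project: Equipment states the collaboration and Hypothesis 3 uses the data.
5. Preliminary and Previous Results reports a study by the group that examined glycated haemoglobin and renal failure together, so the group already handles the two jointly.
6. Two further sources may bear on prior renal status: the NPR, and the clinical information that the SCDR gathered up to 2010. The variables in the latter are not described, and neither source clearly replaces HbA1c or albumin values.

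**What if the NDR were left out?** Take one binary confounder (albuminuria) with hazard ratio HR for ESRD, prevalence p1 in the exposed and p0 in the unexposed, and a true exposure hazard ratio of 1. Every input is assumed.

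Bias factor = (p1·HR + 1 − p1) / (p0·HR + 1 − p0)

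| Exposure | p1 | p0 | HR | Bias factor |
|---|---|---|---|---|
| Antihypertensives | 0.30 | 0.20 | 2 | 1.3/1.2 = 1.08 |
| Antihypertensives | 0.60 | 0.10 | 20 | 12.4/2.9 = 4.28 |
| Pregnancy | 0.05 | 0.20 | 20 | 1.95/4.8 = 0.41 |
| Pregnancy | 0.05 | 0.20 | 2 | 1.05/1.20 = 0.88 |
| Pregnancy | equal | equal | any | 1.00 |
| Pregnancy | 0.20 | 0.05 | 2 | 1.20/1.05 = 1.14 |
| Pregnancy | 0.20 | 0.05 | 20 | 4.8/1.95 = 2.46 |

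The upper antihypertensive value needs all three inputs at their extremes. The pregnancy range includes 1, so not even its direction is known.

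**Life table.** Assume an ESRD hazard of 0.002 per year, a death hazard m, and 25 years at risk. With deaths censored, the risk is 1 − exp(−0.05) = 0.0488. With death as a competing event, it is 0.002/(0.002 + m) × [1 − exp(−25(0.002 + m))]. This gives 0.0482 at m = 0.001 (overstated by about 1%) and 0.0432 at m = 0.01 (about 13%). It applies only if cumulative risk is reported with deaths censored, which the protocol does not say. The rate of ESRD by duration is validly estimated with deaths as withdrawals, and a life table may equally serve survival on renal replacement therapy, where death is the event.

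**Cost of adjusting.** If a fraction f of ESRD events fell within NDR coverage, intervals on the log hazard ratio scale would widen by 1/√f: 1.12 at f = 0.8, 1.41 at 0.5 and 1.83 at 0.3. Coverage is not stated, so these fractions are assumed too. Analysts would have to weigh this cost with the data in hand.

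**The case for a change.** The strongest reply is that choosing covariates can wait for an analysis plan but securing a data source cannot. The authors attach registers to Hypothesis 2 one at a time, each with a purpose, and the one that holds the key confounders is absent. In Equipment the NDR is set apart from the linked registers and described only as a collaboration. Claiming that prescription records will allow drug effects to be studied promises more than such records can deliver alone, and the analysis was due to start in early 2026.

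Part of this stands. The NDR is indeed not named under Hypothesis 2, and a reader cannot tell from that text whether its measurements will be used. The principle is also right: without measurements taken before exposure, neither estimate deserves a causal reading.

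The step from not named to not available does not stand. Hypothesis 3, in the same project and partly with the same SRR outcomes, relies on NDR data. Nor does the proposal of time-dependent exposures with time-updated confounders add a new direction. It is one ordinary way of carrying out the causal survival analysis already announced.

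**Conclusion.** The concern does not call for a change. Hypothesis 2 is brief about its data, but it states nothing wrong, contradicts nothing elsewhere in the protocol and fixes no poor analysis. The missing detail (which NDR measurements, taken when, used how) is what an analysis plan usually supplies, and a group that announces causal survival methods and already works with NDR data can be expected to supply it. A sentence naming the NDR under Hypothesis 2 would help readers, but the plan is not defective without it.

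This conclusion rests on reading the register list as open, which the treatment of HbA1c under Hypothesis 4 supports. If the medication and pregnancy estimates were in fact produced without such measurements, they should be reported as associations not adjusted for indication or prior status. The bias could then be anything from negligible to several-fold, but those figures come from assumed inputs and say nothing about this cohort. The life-table point depends on a use of the method that the protocol does not state, and it falls away for the same reason.
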